**5.0 LIST OF ABBREVIATIONS**

Abbreviation or Term^1	Definition/Explanation
AE	Adverse event
ALT	Alanine aminotransferase
ALK	Anaplastic lymphoma kinase
APTT	Activated partial thromboplastin time
$\alpha$ -KG	$\alpha$ -ketoglutarate
AST	Aspartate aminotransferase
AUC	Area under the concentration-time curve
$\beta$ -HCG	Beta-human chorionic gonadotropin
BID	Twice daily
BIDf	Twice daily – fed cohort
BP	Blood pressure
BUN	Blood urea nitrogen
Ca ++	Calcium
CBC	Complete blood count
ccRCC	Clear Cell Renal Cell Carcinoma
CFR	Code of Federal Regulations
CI	Confidence interval
Cl 	Chloride
CL cr	Creatinine clearance
C max	Maximum observed concentration
CNS	Central nervous system
CR	Complete remission
CTA	Clinical Trial Agreement
CT	Computed tomography
CTCAE	Common Toxicity Criteria for Adverse Events
CV	Coefficient of variation
CYP450	Cytochrome P450
D/C	Discontinue
DFS	Disease-Free Survival
DLBCL	Diffuse Large B-Cell Lymphoma
DLT	Dose Limiting Toxicity
DOR	Duration of Response
ECG	Electrocardiogram
eCRF	Electronic Case Report Form
EDC	Electronic data capture
EORTC	European Organization for Research and Treatment of Cancer
EOT	End of Treatment

Abbreviation or Term 	Definition/Explanation
FDA	Food and Drug Administration
EF	Ejection fraction
FFPE	Fresh Frozen Paraffin Embedded
FH	Fumarate hydratase
FISH	Fluorescence in situ hybridization
FLC	Free light chain
GAC	Glutaminase C, alternative splice variant of glutaminase
GCP	Good Clinical Practice
g/dL	Grams per decilitre
GFR	Glomerular filtration rate
GIST	Gastrointestinal stromal tumor
GGT	Gamma glutamyl transpeptidase
GLP	Good Laboratory Practice
GLS	Glutaminase gene signature
GLS2	Glutaminase 2 (liver form of glutaminase)
GMP	Good Manufacturing Practice
Hb	Hemoglobin
HCO 3 	Bicarbonate
hERG	Human Ether-à-Go-Go Related Gene
HIV	Human immunodeficiency virus
HNSTD	Highest non-severely toxic dose
HPLC	High-performance liquid chromatography
HP-β-CD	Hydroxypropyl-β-cyclodextrin
HR	Heart rate
Hr	Hour or hours
IC 50	Half maximal inhibitory concentration
IEC	Independent Ethics Committee
INR	International Normalized Ratio
irAE	Immune-related Adverse Event
IRB	Institutional Review Board
IRC	Independent Radiology Committee
iRECIST	modified RECIST 1.1 for immune-based therapeutics
irSD	Immune-related Stable Disease
IU	International Unit
IV	Intravenous, intravenously
KGA	Kidney glutaminase (alternative splice variant of glutaminase)
LDH	Lactate dehydrogenase
LFT	Liver Function Test

Abbreviation or Term 	Definition/Explanation
LC-MS/MS	Liquid chromatography-mass spectrometry/mass spectrometry
mAb	Monoclonal Antibody
mcL/ $\mu$ L	Microliter
MedRA	Medical Dictionary for Drug Regulatory Activities
MEL	Melanoma
mL	Milliliter
MTD	Maximum tolerated dose
NSCLC	Non-small cell lung cancer
ORR	Overall response rate
OS	Overall Survival
PD-1	Programmed cell death protein 1
PD-L1	Programmed death ligand 1
PDn	Pharmacodynamic(s)
PFS	Progression Free Survival
PK	Pharmacokinetic(s)
PO	Per os (administered by mouth)
PR	Partial response
PSA	Prostate specific antigen
PT	Prothrombin time
aPTT	Activated Partial thromboplastin time
QTcF	Corrected QT interval, Fridericia's formula
RP2D	Recommended Phase 2 Dose
RBC	Red Blood Cell
RCC	Renal cell carcinoma
Rx	Treatment
SAE	Serious adverse event
SD	Stable disease
SDH	Succinate dehydrogenase
SFLC	Serum free light chain
SGOT	Serum glutamic oxaloacetic transaminase
SGPT	Serum glutamic pyruvic transaminase
STD 10	Severely toxic dose in 10% of animals
T max	Time of maximum observed concentration
TEAE	Treatment-emergent adverse event
TCA	Tricarboxylic acid
TID	Three times daily
TIDf	Three times daily – fed cohort
TNBC	Triple negative breast cancer

Abbreviation or Term 	Definition/Explanation
ULN	Upper limit of normal
ULQ	Upper limit of quantitation
WBC	White blood cell

1 All of these abbreviations may or may not be used in protocol.

**6.0 CORE PROTOCOL****6.1 Objectives**

Primary Objectives	Primary Endpoints
To evaluate the safety and tolerability of CB-839 in combination with nivolumab for patients with advanced/metastatic clear cell Renal Cell Carcinoma (ccRCC), melanoma (MEL), and Non-Small Cell Lung Cancer (NSCLC)	Evaluation of clinical tolerability of CB-839 in combination with nivolumab, including dose intensity of CB-839, adverse events, and laboratory data
To evaluate anti-tumor effect of CB-839 in combination with nivolumab for patients with advanced/metastatic ccRCC, MEL, and NSCLC as assessed by investigator	Overall response rate (ORR) and duration of response (DOR) per Investigator assessed Response Evaluation Criteria in Solid Tumors (RECIST) v1.1
To evaluate anti-tumor effect of CB-839 in combination with nivolumab for patients with advanced/metastatic MEL by Independent Radiology Committee (IRC)	Overall response rate (ORR) and duration of response (DOR) by Independent Radiology Committee (IRC)-assessed Response Evaluation Criteria in Solid Tumors (RECIST) v1.1
Secondary Objectives	Secondary Endpoints
To select the recommended Phase 2 dose (RP2D) of CB-839 in combination with nivolumab for patients with advanced/metastatic ccRCC, MEL, and NSCLC	Based on an evaluation of adverse events, pharmacokinetics, pharmacodynamics and evidence of clinical activity
To evaluate the progression-free survival (PFS) and overall survival (OS) of CB-839 in combination with nivolumab for patients with advanced/metastatic ccRCC, MEL, and NSCLC by standard RECIST criteria	Assessed by progression-free survival (PFS) per RECIST v1.1 and overall survival (OS)
To evaluate anti-tumor effect of CB-839 as monotherapy in patients with advanced/metastatic MEL	Assessed by ORR, DOR and PFS per RECIST v1.1
Determine pharmacokinetics (PK) of CB-839 in combination with nivolumab	Non-compartmental method of analysis will be used to analyze the plasma concentrations of CB-839
Exploratory Objectives	Exploratory Endpoints
To evaluate the pharmacodynamic effects of CB-839 alone and in combination with nivolumab in patients with advanced/metastatic ccRCC, MEL, and NSCLC	To include evaluation of changes in peripheral blood immunophenotyping, tumor immune infiltrate and plasma glutamine levels
To investigate the relationship between PK, pharmacodynamic biomarkers and anti-tumor activity	Analysis of any potential relationship between drug exposure, pharmacodynamics biomarkers and/or anti-tumor effect

To evaluate biomarkers that may predict the anti-tumor effect of CB-839 alone and in combination with nivolumab in patients with advanced/metastatic ccRCC, MEL, and NSCLC	Analysis of any potential relationship between predose biomarkers of tumor or immune state and anti-tumor effect, including PD-L1 expression in tumor
To evaluate anti-tumor effect of CB-839 as monotherapy in patients with advanced/metastatic MEL by modified RECIST 1.1 for immune-based therapeutics (iRECIST)	Assessed by ORR, DOR and PFS per iRECIST
To evaluate anti-tumor effect of CB-839 in combination with nivolumab for patients with advanced/metastatic ccRCC, MEL, and NSCLC by iRECIST	Assessed by ORR, DOR and PFS per iRECIST
To evaluate anti-tumor effect of CB-839 and nivolumab in combination after progression on CB-839 monotherapy in patients with advanced/metastatic MEL	Assessed by ORR, DOR and PFS per RECIST v1.1 and by iRECIST

## 6.2 Sample Size

[figure not shown]
Dose Escalation: A minimum of 9-12 patients with ccRCC, melanoma, or NSCLC will be enrolled in Dose Escalation. Patients that are considered not evaluable for DLT assessment ([Section 16.4.2](#)) will be replaced. Up to 6 additional patients may be enrolled at each dose level to further investigate safety and pharmacodynamic biomarkers.

Dose Expansion: Approximately 92 patients will be enrolled in Stage 1 across six cohorts. If a patient does not meet criteria for inclusion into the Efficacy Evaluable Population ([Section 16.5](#)), the patient will be considered not evaluable for efficacy and will be replaced. If any cohorts achieve the pre-defined Stage 1 thresholds for clinical activity, additional patients will be enrolled in Stage 2 for that Cohort. Approximately 195 patients will be enrolled in Stage 2 across six cohorts if all complete enrollment. The number of patients may be increased in Stage 2 in each expansion cohort based upon observed anti-tumor activity.

## 6.3 Study Design

Protocol CX-839-004 is a Phase 1/2 open-label study of the combination of CB-839 with nivolumab in patients with advanced/metastatic ccRCC, MEL, and NSCLC, as well as CB-839 monotherapy in patients with advanced/metastatic MEL. Sequential dose escalation of CB-839 with full dose nivolumab (CB-Nivo) will take place in patients with advanced ccRCC,

advanced/metastatic MEL, or metastatic NSCLC. Subsequently, multiple disease-specific single-arm cohorts will be enrolled in which CB-839 will be administered in combination with the full approved dose of nivolumab. CB-839 will be administered at the RP2D established in dose escalation. Patients in dose escalation must be eligible for one of the dose expansion cohorts. CB-839 monotherapy will be administered at the previously established monotherapy RP2D of 800 mg PO BID.

### 6.3.1 Phase 1 - Dose Escalation

Dose escalation will use a 3+3 design and will enroll cohorts of 3-6 patients with advanced ccRCC, advanced/ metastatic MEL, or metastatic NSCLC at escalating doses as outlined in Table 6.3-1. Patients will receive escalating doses of CB-839 in combination with the FDA-approved anti-PD-1 agent nivolumab. Nivolumab will be administered at the FDA-approved dose of 240 mg every 2 weeks without adjustment for body weight.

Dose escalation will continue until identification of a MTD or up to a maximum dose of 800 mg orally BID. Up to 6 additional patients may be enrolled to a dose escalation cohort in order to generate additional safety, pharmacokinetic, and biomarker data.

The starting dose of CB-839 will be 600 mg BID and the maximum dose will be 800 mg BID. The first dose of CB-839 will be administered in the morning with breakfast. The second dose will be administered in the evening with a meal approximately 12 hr ( $\pm$  2 hr) after the morning dose. The dose range and schedule were selected based on the results of three Phase 1 studies of CB-839: CX-839-001 (solid tumors), CX-839-002 (multiple myeloma and non-Hodgkin's lymphoma), and CX-839-003 (acute leukemia) in which doses up to 1000 mg BID were administered without identification of an MTD. The dose of 600 mg BID with food has been well tolerated and has resulted in good exposure that achieves robust inhibition of glutaminase activity in platelets and tumors. A monotherapy expansion cohort in CX-839-001 is currently being enrolled at the 800 mg BID dose and has been tolerated to date.

Cohorts of three to six patients with ccRCC, MEL, or NSCLC will receive CB-839 capsules (200 mg strength) or tablets (200 mg strength) in a dose-escalating fashion together with full dose nivolumab according to the rules presented below (Table 6.3-1). To be enrolled in dose escalation, each patient must fulfill the eligibility criteria for one of the Expansion Cohorts described in the Cohort Expansion section below.

**Table 6.3-1: Dose Escalation**

Cohort	CB-839 Capsules or Tablets			Nivolumab
	Dose (mg) BID	% Increase	N	Dose (mg) Q2W
-1	400	-50%	3 – 6	240
1*	600		3 – 6	240
2	800	33%	6	240

\*starting dose level

### 6.3.1.1 Dose Escalation Rules

Dose limiting toxicities (DLTs) observed in Cycle 1 (first 28 days of dosing) will be used to determine escalation to the next dose level. The study is using a traditional 3+3 design and the dose escalation rules are as follows:

- An initial cohort of 3 patients is enrolled.

- If 0/3 patients develops a DLT, escalation to the next dose will occur.
- If 1/3 patients develops a DLT:
  - Another 3 patients will be enrolled at this dose level.
    - If 0 of the 3 new patients develops a DLT (for a total of 1/6 patients with a DLT at this dose level), escalation to the next dose level will occur.
    - If  $\geq 1$  of the 3 new patients develops a DLT (for a total of  $\geq 2/6$  patients with a DLT at this dose level), the dose escalation stage of the trial will be terminated and the dose directly below the current dose will be considered the MTD.
- If  $\geq 2/3$  patients develop a DLT, the dose escalation stage of the trial will be terminated and the dose directly below the current dose will be considered the MTD.

The highest planned dose of CB-839 to be tested during dose escalation is 800 mg BID. If 0/3 patients or  $\leq 1/6$  patients develop a DLT at that dose, then 800 mg BID of CB-839 in combination with nivolumab (240 mg IV every 2 weeks) will be considered the Recommended Phase 2 Dose (RP2D) of the combination. If  $\geq 2/6$  patients develop a DLT at the 800 mg BID dose level, then 600 mg BID will be considered the RP2D, as long as a total of  $< 2/6$  patients develops a DLT at that dose. If a dose level below 800 mg BID is selected as the MTD due to only 2 DLTs and subsequent clinical data demonstrate the DLT rate at the MTD to be  $< 10\%$  in  $> 10$  patients, re-escalation of the previous dose associated with DLT may be considered. If re-escalation occurs, up to 6 additional patients may be enrolled and the dose level will be considered tolerable if the DLT rate is  $< 33\%$ .

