#### **6.3.1.3 Definition of Maximum Tolerated Dose (MTD):**

The Maximum Tolerated Dose (MTD) is defined as the highest dose level with no more than 1 DLT reported in 6 DLT-evaluable patients.

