#### **6.3.1.4 Definition of Recommended Phase 2 Dose (RP2D):**

The Recommended Phase 2 Dose (RP2D) of CB-Nivo will be selected based on the clinical data and will not exceed the MTD. If  $< 2/6$  patients experience a DLT at 800 mg BID during dose escalation, then 800 mg BID will be considered to be the RP2D. If  $\geq 2/6$  patients experience DLTs at 800 mg BID, and  $\leq 1/6$  patients experience a DLT at 600 mg BID, then 600 mg BID will be considered the RP2D. The Sponsor, in consultation with the Study Investigators, will continue to evaluate the safety data accumulated during the evaluation of dose expansion cohorts and may amend the RP2D with further experience.

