## 16.3 Sample Size and Power

**Dose Escalation:** The goal is to determine a dose level of CB-839 for which the rate of DLTs is less than 33%. A minimum of 9-12 patients are planned for Dose Escalation.

**Dose Expansion:** For Cohorts 1-6, Simon's two-stage design ([Simon 1989](#)) will be used as outlined in [Table 22.2-1](#) below. The null hypothesis that the response rate is [ p0 ] will be tested against a one-sided alternative. In the first stage, [ n1 ] patients will be accrued. If there are [ r1 ] or fewer responses in these [ n1 ] patients, the study will be stopped. Otherwise, [ n - n1 ] additional patients will be accrued for a total of [ n ]. The null hypothesis will be rejected if [ r2 + 1 ] or more responses are observed in [ n ] patients. This design yields a type I error rate of 0.1 and power of 80% when the true response rate is [ p1 ].

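### Section 6.3.1.1 lets 800 mg BID be declared the RP2D on 0/3 DLTs, although Table 6.3-1 and the 9-12 patient minimum plan six patients at that dose

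*Protocol*

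**What the plan says.** Protocol Section 6.3.1.1 sets the rule at the top dose: "The highest planned dose of CB-839 to be tested during dose escalation is 800 mg BID. If 0/3 patients or" at most 1 of 6 patients have a DLT there, 800 mg BID plus nivolumab is the RP2D of the combination.

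Four other places deal with the number of patients at that dose.

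- Table 6.3-1 gives N = 3-6 at 400 mg and 600 mg, but a single value, 6, at 800 mg.
- Protocol Section 6.2 says "A minimum of 9-12 patients with ccRCC, melanoma, or NSCLC will be enrolled in Dose Escalation". Protocol Section 16.3 and SAP Section 5.3 repeat the figure.
- Section 6.3.1.3 defines the MTD as the "highest dose level with no more than 1 DLT reported in 6 DLT-evaluable patients".
- Section 6.3.1.4 says the RP2D "will be selected based on the clinical data and will not exceed the MTD". It then gives the 800 mg rule on six patients: if fewer than 2/6 "patients experience a DLT at 800 mg BID during dose escalation, then 800 mg BID will be considered to be the RP2D".

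The general text in Protocol Section 6.3.1 describes cohorts of 3-6 and refers to Table 6.3-1 for detail. SAP Section 5 says 3-5 and refers to the same table. The SAP repeats the MTD definition and the cap at the MTD, but not the 0/3 option.

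**The concern.** In the ordinary steps of Section 6.3.1.1, 0/3 permits escalation to the next level. At 800 mg there is no next level, so the same result is used to settle the dose for the combination expansion cohorts. The rest of the plan provides for six patients at that point. Table 6.3-1 uses a range where three may suffice and does not use one at 800 mg.

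The rule can also contradict itself. Suppose the 800 mg cohort starts with 0/3, fills to six as the table plans, and two or three of the next three patients have a DLT. One sentence of Section 6.3.1.1 has already made 800 mg the RP2D. The next sentence, triggered by 2/6 or more, makes 600 mg the RP2D provided fewer than 2/6 had a DLT there. The text does not say which prevails.

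At stake is how much DLT information must stand behind the combination dose before expansion, and whether two readers would apply the same threshold.

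**Working it through.** **Planned size.** The inputs are the cohort sizes in Table 6.3-1 for the two planned levels, 600 mg (3-6) and 800 mg (6).

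- Lower end: 3 + 6 = 9. Upper end: 6 + 6 = 12. This reproduces the stated 9-12 exactly.
- If three patients at each level were enough, the lower end would be 3 + 3 = 6, which does not match. The stated minimum therefore presupposes six patients at 800 mg.

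**Acceptance of 800 mg once that level is opened.** Let p be the true DLT rate at 800 mg and q = 1 - p. The documents give no DLT rate for the combination, so each p below is an assumption. One third corresponds to the 33% bound in Section 16.3.

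- Rule as written (0/3, or 1/3 followed by 0/3): A = q³ + 3pq² × q³.
- At most 1 DLT in six: B = q⁶ + 6pq⁵.

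| Assumed p | A | B | A - B |
|---|---|---|---|
| 10% | 0.7290 + 0.2430 × 0.7290 = 0.9061 | 0.8857 | 0.0204 |
| 20% | 0.5120 + 0.3840 × 0.5120 = 0.7086 | 0.6554 | 0.0532 |
| 1/3 | 0.2963 + 0.4444 × 0.2963 = 0.4280 | 0.3512 | 0.0768 |

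**Cross-check.** The two rules differ only when 0/3 is followed by at least 2 DLTs in the next three, so A - B = P(0 of 3) × P(at least 2 of 3):

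- 10%: 0.7290 × 0.0280 = 0.0204
- 20%: 0.5120 × 0.1040 = 0.0532
- 1/3: 0.2963 × 0.2593 = 0.0768

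The gap is therefore about 2, 5 and 8 percentage points. It assumes that an RP2D call made on 0/3 stands.

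**A lower rate.** Table 10.7-2 gives 3/66 = 4.5% drug-related Grade 3 or higher events on BID monotherapy. Used as an assumed DLT rate, the gap is 0.8697 × 0.0060 = 0.0052, about half a point. This is only a low anchor, because it is not a DLT rate and leaves out nivolumab.

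**From the start of escalation.** If the rate is the same at 600 mg and 800 mg, the gap is A × (A - B):

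- 10%: 0.9061 × 0.0204 = 0.0185
- 20%: 0.7086 × 0.0532 = 0.0377
- 1/3: 0.4280 × 0.0768 = 0.0329

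**How often three patients carry the decision.** The share of acceptances resting on 0/3 is q³/A: 0.80, 0.72 and 0.69 at the three rates.

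**The case against.** The strongest reply is that the provisions can be read together. Section 6.3.1.1 says when 800 mg is considered the RP2D. It does not say that enrolment at 800 mg stops at three. Table 6.3-1 and the 9-12 minimum can still be met if the cohort fills to six after the call. A reader might infer that escalation would end with 6 patients, but that follows only if the table and the minimum are set aside, so no probability is attached to it here. What remains is that the threshold for the decision is still three patients, and the text does not say what happens if the next three show DLTs.

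A reader might also infer a plain breach of the MTD cap, since 0/3 cannot meet a six-patient definition. The documents do not go that far. Section 6.3.1 lets escalation finish at 800 mg without an MTD being identified, and the fewer-than-2/6 wording in Section 6.3.1.4 is a sufficient condition, not an only-if. These sections support the point but do not carry it alone.

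Nor is it an anomaly that "then 600 mg BID will be considered the RP2D, as long as a total of" fewer than 2/6 have a DLT at 600 mg. That condition applies only after DLTs at 800 mg, and asking for six patients then is ordinary 3+3 practice.

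Finally, expansion was under way. Section 6.3.2.4 reports 16 evaluable Cohort 4 patients, and the footnote to Table 22.2-1 says its Stage 1 was complete. Optional backfill and continuing safety review, with power to amend the RP2D, also lower the risk. All of this limits the practical effect. Neither safeguard is tied to the RP2D call, so neither settles which threshold governs.

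**Conclusion.** The point holds as an inconsistency in a decision rule. The 0/3 option at 800 mg conflicts with N = 6 in Table 6.3-1 and with the 9-12 minimum, and it does not match the six-patient basis of Sections 6.3.1.3 and 6.3.1.4. Under assumed DLT rates of 10%, 20% and one third, it raises the chance of accepting 800 mg by about 2, 5 and 8 points once that level is opened. The gain is smaller at lower rates and when counted from the start of escalation. It is worth correcting, but the practical effect at this stage is small.

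It would be tempting to conclude that the RP2D in use rests on three patients, or that the plan fails to state it. Neither conclusion is supported. The number of patients who cleared the dose is a matter of conduct, and figures are missing from the supplied text, including possibly the design schema.

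**What to change.** In Section 6.3.1.1, delete the 0/3 option from the 800 mg sentence. The RP2D call at that dose would then need at most 1 DLT in 6 DLT-evaluable patients, as Table 6.3-1 already plans. This costs one clause and adds no patients beyond the stated size.

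If 800 mg was cleared on three patients, do not reopen escalation. Confirm at most 1/6 using backfill patients or patients already treated with the combination at 800 mg. Section 17.2 has AEs followed from the start of treatment, so Cycle 1 AE data should be available. AE follow-up is not DLT adjudication, however. The check needs a small retrospective review of evaluability (at least 75% of CB-839 doses and both nivolumab doses in Cycle 1) and of events against the DLT criteria in Section 6.3.1.2.

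As a separate tidy-up, align the cohort size of 3-5 in SAP Section 5 with Table 6.3-1. A maximum of five cannot hold the six-patient step of the 3+3 rule.

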### 6.3.1.2 Dose-Limiting Toxicity

During dose escalation, patients must receive at least 75% of the planned CB-839 administrations and both doses of nivolumab in the first 28-day treatment cycle to be considered evaluable for DLT, unless the patient has a DLT or has the study drug held for an adverse event (AE) that may herald a DLT. Patients who discontinue the study during the first cycle prior to receiving the requisite study treatment administrations for reasons that include, but are not limited to, clinical/radiographic progression, voluntary withdrawal, or complications that the Principal Investigator considers secondary to the patient's malignancy will not be considered evaluable for DLT and will be replaced.

It is likely that expected Grade 3 AEs associated with nivolumab administration will occur in this study and given the small sample size of cohorts this may occur by chance in 2 of 6 patients, the usual threshold for unacceptable toxicity. It will be important to differentiate between immune-related adverse events (irAEs) expected from nivolumab toxicity as opposed to an increase in frequency or a worsening of severity of irAEs as an indicator of unacceptable toxicity related to the combination.

The occurrence of any of the following toxicities during Cycle 1 will be considered a DLT, if judged by the Investigator to be related (possibly or probably) to study drug administration:

Non-Hematologic DLT:

- Any  $\geq$  Grade 4 non-hematological toxicity
- Grade 3 non-hematologic toxicity lasting  $> 3$  days despite optimal supportive care with the exception of:
  - Grade 3 fatigue
  - Grade 3 rash or itching that resolves to  $\leq$  Grade 1 within 3 weeks
  - Grade 3 tumor flare (defined as local pain, irritation or rash localized at sites of known or suspected tumor)
  - Grade 3 irAE that resolves to Grade 1 with corticosteroid therapy in  $\leq 3$  weeks
  - A transient (resolves within 6 hours of onset) Grade 3 infusion-related AE
  - Grade 3/4 elevation in serum amylase and/or lipase that are not associated with clinical or radiological evidence of pancreatitis
- Any clinically meaningful Grade 3 non-hematologic laboratory value if:
  - Medical intervention (other than electrolyte repletion) is required to treat the patient, OR
  - The abnormality leads to hospitalization, OR
  - The abnormality persists for  $>1$  week.

Hematologic DLT:

